12.4 Early Withdrawal of Subjects

- If the subject fails to comply with the defined treatment plan and follow-up evaluations, the subject may be removed from the study at the discretion of the treatment investigator
- If the subject withdraws consent for continued participation, he/she will be removed from the study
- If the subject develops significant, new neurologic deficits or a change in level of consciousness a CT or MR scan may be performed to evaluate for hemorrhage/edema. If symptoms remain unmanageable by medications, craniotomy may be performed for resection of tumor, necrosis, or hemorrhage if medically indicated
- The reason for study removal and the date the subject was removed should be documented in the Case Report Form (CRF)
- If the treatment related toxicity experienced toxicity (Grade 2 or higher) persists for more than 21 days or ≥1 Dose Limiting Toxicity, the subject will not have the subsequent FUS and early withdrawal will be considered.

The primary endpoint of this study is safety. As such, subjects will be withdrawn from the study as per the guidelines outlined above. Should similar toxicities occur in more than one subject; early interruption of the study will be considered.

12.5 Data collection and follow-up for withdrawn subjects

Even though subjects may be withdrawn prematurely from the study, it is imperative to collect at least survival data on such subjects throughout the protocol, defined follow-up period (though careful thought should be given to the full data set, which should be collected on such subjects to fully support the analysis). Such data is important to the integrity of the final study analysis since early withdrawal could be related to the safety profile of the study drug. If a subject withdraws consent to participate in the study, attempts will be made to obtain consent from the subject to record at least survival data up to the protocol-described end of the subject follow-up period. It must be a high priority to try to obtain at least survival data on all subjects lost to follow-up and to note what methods should be used before one can state the subject is truly lost to follow-up (e.g. number of phone calls to subject, phone calls to next-of-kin if possible, certified letters, etc.). Subjects who have received study drug and are withdrawn because of unacceptable adverse events will be followed until resolution or stabilization of the adverse event.

12.6 Stopping Rules

Redundant safety features have been added to the hardware of the device, as grounding for the transducer, safety switch for the amplifier and function generator. Additionally, we will incorporate safety valves in our software. For any signs showing safety risk including high cavitation dose in the acoustic monitoring or unstable vital signs, the device can be stopped from the computer user interface and/or an emergency stop button. Treatment will be stopped in the case of any reaction of the subject to the ultrasound exposure or microbubble infusion. Pulse oximetry will be used during MRI scans to mitigate the risk of anaphylactic reaction to MRI contrast agents.

The investigation will be terminated in case of any death, life threatening event, or any other serious adverse event (including disability or clinically significant manifestation of local hemorrhage or edema) due to the procedure. An episode of status epilepticus during treatment will terminate the session immediately.

If the selected ultrasound settings (i.e., MI of 0.4) do not successfully open the BBB in 3 subjects, FDA will be contacted via a submission of an IND supplement, to discuss revising the protocol's focused ultrasound parameters.

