3.1.4 Risks Associated with Panobinostat

The most common adverse reactions (incidence of at least 20%) in clinical studies are diarrhea, fatigue, nausea, peripheral edema, decreased appetite, pyrexia, and vomiting.

The most common non-hematologic laboratory abnormalities (incidence $\geq 40\%$) are: Hypophosphatemia, hypokalemia, hyponatremia, and increased creatinine.

The most common hematologic laboratory abnormalities (incidence $\geq 60\%$) are: thrombocytopenia, lymphopenia, leukopenia, neutropenia, and anemia.

Panobinostat carries a boxed warning alerting patients and health care professionals that severe diarrhea and severe and fatal cardiac events, arrhythmias and electrocardiogram (ECG) changes have occurred in patients receiving Panobinostat.

Other notable adverse drug reactions of Panobinostat not described above, which were either clinically significant, or occurred with a frequency less than 10% but had a frequency in the Panobinostat arm greater than 2% over the control arm in the multiple myeloma clinical trial are listed below:

Infections and infestations: hepatitis B.

Endocrine disorders: hypothyroidism.

Metabolism and nutrition disorders: hyperglycemia, dehydration, fluid retention, hyperuricemia, hypomagnesemia.

Nervous system disorders: dizziness, headache, syncope, tremor, dysgeusia.

Cardiac disorders: palpitations.

Vascular disorders: hypotension, hypertension, orthostatic hypotension.

Respiratory, thoracic and mediastinal disorders: cough, dyspnea, respiratory failure, rales, wheezing.

Gastrointestinal disorders: abdominal pain, dyspepsia, gastritis, cheilitis, abdominal distension, dry mouth, flatulence, colitis, gastrointestinal pain.

Skin and subcutaneous disorders: skin lesions, rash, erythema.

Musculoskeletal and connective tissue disorders: joint swelling.

Renal and urinary disorders: renal failure, urinary incontinence.

General disorders and administration site conditions: chills.

Investigations: blood urea increased, glomerular filtration rate decreased, blood alkaline phosphatase increased.

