 - If 1 DLT is noted during pre-cycle 5 follow-ups and MRI (without contrast), the subject will discontinue treatments and will come off the study (please refer to [section 12.3](#) for Early Stopping Guidelines). Other subjects may continue to enroll.
 - If 2 DLTs are noted at the same NOTS level, enrollment will be halted following Early Stopping Guidelines detailed in [Section 12.3](#).
- If 0 DLTs are noted during pre-cycle 6 MRI (without contrast) and follow-up, the subject will continue to receive FUS treatment at 3 tumor sites (NOTS Level C) in the 6th cycle.
 - If 1 DLT is noted during pre-cycle 6 follow-ups and MRI (without contrast), the subject will discontinue treatments and will come off the study (please refer to [section 12.3](#) for Early Stopping Guidelines). Other subjects may continue to enroll.
 - If 2 DLTs are noted at the same NOTS level, enrollment will be halted following Early Stopping Guidelines detailed in [Section 12.3](#).

Within each cycle, if 1 DLT is noted the subject will discontinue treatments and will come off the study (please refer to [section 12.3](#) for Early Stopping Guidelines). Other subjects may continue to enroll.

If 2 DLTs are noted at the same NOTS level for a subject, study enrollment will be halted following Early Stopping Guidelines detailed in [Section 12.3](#).

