7.3 Investigational Plan

Subjects' preoperative MRI and their history will be reviewed at the weekly CUIMC Pediatric Neuro-Oncology Tumor Board to determine disease status, and to confirm eligibility criteria and to schedule the admission date. A recent (no longer than 7 days prior to the time of the procedure) MRI with and without Gadolinium contrast that includes T1, T2, and FLAIR is required, otherwise the MRI will have to be repeated.

On the day of admission, the subject will present to the Pediatric Oncology Outpatient clinic and will be brought to the Radiation Oncology Suite (for the Navigator-Guided Focused Ultrasound (NgFUS)) (Children Hospital of New York (CHONY) Floor 3) and subsequently to the Pediatric Oncology outpatient clinic (HIP-7). Institutional policies regarding COVID for transportation will be followed.

Columbia University Irving Medical Center
Protocol Version 4.0 Date: 12.10.2021

In the radiation oncology suite, under the supervision of the Pediatric Oncology and Radiation Oncology teams, the subject will undergo:

- Focused Ultrasound and injection of DEFINITY® Microbubbles using the NgFUS system with the following ultrasonic parameters and microbubble dose:

Table I: NgFUS treatment parameters

| | |
|------------------------------------|----------------------------------------|
| FUS frequency | 0.25 MHz |
| Acoustic pressure | 200 kPa _{pk-neg} |
| Pulse length | 2,500 cycles or 10 ms |
| Pulse repetition frequency | 2 Hz |
| Total sonication time per location | 2 min |
| Definity microbubble dose | 10 µl/kg |
| Number of Tumor sites | Level A: 1 Level B: 2 Level C: 3 |

[figure not shown]
FUS will be aimed for non-enhancing peritumoral areas. Even if there is some contrast enhancement before FUS, this should be clearly increased following FUS. The focal area is quite big (6mm x 6mm x 49mm), so there should be clear opening in the neighboring non-enhancing tissue.

The total estimated time for the FUS procedure is 30-45 min.

Subjects will be sonicated, according to the pre-treatment MRI. Following the NgFUS procedure, subjects will be brought back to the Pediatric Oncology Outpatient clinic where they will receive the oral Panobinostat 15 mg/m².

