12.2 Dose Limiting Toxicities

Dose limiting toxicities (DLT) will be defined as any new (or increased from baseline), treatment related (drug and/or device):

1. Neurological deficits based on neurological examination which are grade 3 or greater nervous system adverse events at least possibly attributed to sonication (as defined by CTCAE v5.0).

2. Grade 2 or higher symptomatic intracranial hemorrhage or stroke.

These deficits include but are not limited to changes in level of consciousness, new onset speech difficulties (aphasia, mutism, dysarthria), confusion, visual field deficits, focal weakness, seizures. The DLT period is defined as starting the day of the first scheduled FUS treatment and lasting until 14 days after the last scheduled FUS treatment.

Furthermore, DLT criteria include any systemic treatment- related Grade 3 or higher hematologic or non-hematologic toxicity within a period of 14 days after the scheduled FUS treatment. Examples of exceptions could include:

- I. Grade 3 thrombocytopenia without bleeding, Grade 3 or 4 lymphopenia, Grade 3 neutropenia without fever.
- II. Nausea, vomiting or diarrhea responding to medical management within 48 hours
- III. Electrolyte disturbances that are asymptomatic and response to supportive care within 48 hours; hyperglycemia \leq 12 hours

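### Sections 7.2/12.1, 12.3, 12.6, 13.2 and 13.3 give incompatible study-level consequences for a single death or life-threatening event related to panobinostat

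*Combined protocol and SAP*

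**What the plan says.** **One-event rule (12.6).** "The investigation will be terminated in case of any death, life threatening event, or any other serious adverse event (including disability", and the last item in full reads "any other serious adverse event (including disability or clinically significant manifestation of local hemorrhage or edema) due to the procedure". The drug is not named. The neighbouring text in 12.6 concerns the device, the microbubbles and the imaging contrast.

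**Meaning of procedure (7.3).** "Following the NgFUS procedure, subjects will be brought back to the Pediatric Oncology Outpatient clinic where they will receive the oral Panobinostat". The sonication and the drug are separate steps here.

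**Toxicity (12.2).** A DLT is "any new (or increased from baseline), treatment related (drug and/or device". Treatment-related systemic toxicity of Grade 3 or higher within 14 days after a scheduled FUS also counts, with listed examples of exceptions.

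**Drug risk (3.1.4).** The boxed warning says that "severe and fatal cardiac events, arrhythmias and electrocardiogram (ECG) changes have occurred in patients receiving Panobinostat".

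**DLT rule (7.2, repeated in 12.1).** "Within each cycle, if 1 DLT is noted the subject will discontinue treatments and will come off the study", and enrolment of others may go on. Enrolment halts at two DLTs at one NOTS level. One sentence in each section says two for a subject, while 12.3 says more than one subject.

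**20% rule (12.3).** The study is discontinued at any time if more than 20% of patients have medical complications. At a true rate of 10%, the stated stopping probabilities are 0.02 for 6 patients and 0.053 for 9.

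**Reactions (13.2, 13.3).** For an allergic or other reaction to the therapy, 13.2 withdraws the subject; 13.3 immediately discontinues the study.

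**The concern.** Safety of FUS combined with panobinostat in children is the primary question, and the drug is given on FUS treatment days. A fatal or life-threatening drug reaction is a harm the protocol itself foresees, so an investigator or DSMC member should be able to read off what happens to the study when the first one occurs.

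They cannot. Depending on the section consulted, the answer is termination, immediate discontinuation, removal of one subject with enrolment continuing, or a percentage rule whose terms are not defined. At stake is whether further children are enrolled after such an event without a required hold, and whether two readers of the same protocol would take the same action.

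A smaller ambiguity sits in the same sentence of 12.6. It does not say expressly that its reference to any death leaves out death from DMG.

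**Working it through.** **1. The same event under each section.** Take one death attributed to panobinostat, within the DLT window.

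| Section | Does it apply? | Study-level action |
|---|---|---|
| 12.6 | Not clearly; tied to the procedure, which 7.3 separates from the drug | Termination, if it applies |
| 7.2 / 12.1 | Yes, as one DLT | None; others may enrol |
| 12.3, two-DLT rule | No, only one DLT | None |
| 12.3, 20% rule | Only if a death is a medical complication, and only early | Discontinuation |
| 12.4 | No; needs similar toxicities in more than one subject | Interruption only considered |
| 13.2 | If a death is a reaction to the therapy | None; the subject is withdrawn |
| 13.3 | On the same condition | Immediate discontinuation |

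**2. The 12.3 figures, reproduced first.** Use the binomial tail at a true rate of 10%.
- The rule as worded needs 2 events at N = 6 (2/6 = 33%) and 2 at N = 9 (2/9 = 22%). P(2 or more) = 0.114 and 0.225, which do not match the stated 0.02 and 0.053.
- P(3 or more) = 0.016 and 0.053, which match.

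The printed probabilities therefore fit a rule of three or more events. On the rule as calculated, one death would never stop the study.

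**3. When one event passes 20% as worded.** The denominator is assumed to be subjects treated so far. 1/1 = 100%, 1/2 = 50%, 1/3 = 33% and 1/4 = 25% exceed the limit. 1/5 = 20% does not, nor does any later fraction down to 1/15 = 6.7%.

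**4. Illustration of size.** Assume 15 subjects (the maximum), a drug-death risk q per subject (not in the documents), levels drawn evenly from A, B and C, and deaths as the only DLTs. Let K be the number of drug deaths. At q = 5%:
- P(K ≥ 1) = 1 − 0.95^15 = 0.54. P(K = 1, 2, 3) = 0.366, 0.135, 0.031.
- The chance that no two fall at one level is 1, 2/3 and 2/9. At least one death but no two at one level: 0.366 + 0.135 × 2/3 + 0.031 × 2/9 = 0.46.
- To stay at or below 20% throughout, the first death must be at subject 5 or later, the second at 10 or later, the third at 15. The shares of orderings are 11/15, 45/105 and 35/455. Then 0.366 × 11/15 + 0.135 × 2/3 × 45/105 + 0.031 × 2/9 × 35/455 = 0.31.

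| q | Any drug death | No two at one level | Also never above 20% |
|---|---|---|---|
| 3% | 0.37 | 0.34 | 0.23 |
| 5% | 0.54 | 0.46 | 0.31 |
| 10% | 0.79 | 0.55 | 0.33 |

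Non-fatal DLTs also feed the two-DLT halt. With an assumed non-fatal DLT risk of 10% or 20% per subject, the 0.31 falls to about 0.15 or 0.05. This credits a halt whenever in the trial it occurs, including before the death.

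**The case against.** **Other rules can reach a drug death.** A reader might infer that 12.6 is the only one-event rule, and that a drug-related death never pauses the study. The documents do not support that. Read literally, 13.3 discontinues the study for any reaction to the therapy, and 12.1 uses study therapy in a sense that can include the drug. The 20% rule has no device restriction and could catch one event among the first four subjects. This stands, and it limits the point to about the fifth subject onward. But the 13.3 sentence sits in a paragraph about observation during NgFUS, and 13.2 gives a different action for the same trigger.

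**The event would be reviewed.** A reader might also infer that enrolment would continue unreviewed. That is wrong. Section 11.3.4 sends SAEs that are not unanticipated problems to the DSMC within 24 hours. Section 11.3.2 sends unanticipated problems to the IRB within 1 week, and 11.3.3 sends fatal suspected reactions to the FDA within 7 days. Under 13.3 the DSMC monitors every treated subject, meets twice a month and can require changes. What is missing is a stated hold while that happens. The 14-day wait in 12.3 follows directly on the two-DLT halt; even if it applies generally, it is elapsed time, not review.

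**The first disease death would not plainly end the trial.** If the qualifier in 12.6 governed only the last item, any death would include death from DMG. Taking the 9-month median in 2.1 as exponential survival from entry, the 6-month death risk is 1 − 2^(−6/9) = 0.37, and P(at least one death) is 0.999 with 15 subjects. But the natural reading applies the qualifier to the whole list, so this is an ambiguity to remove, not the plan's evident meaning.

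**A deliberate choice.** Going on after one DLT is ordinary in a 3+3 design. A sponsor may reasonably use one-event termination for the investigational device and DLT counting for a drug whose toxicity profile 6.1 calls known. That is a fair defence of 7.2 and 12.1, but the protocol does not state that division, and 13.3 cuts across it.

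**Conclusion.** The point holds as an inconsistency between sections, not as the absence of any safeguard. For one panobinostat-related death or life-threatening event, the stated study-level actions range from none to immediate discontinuation. From about the fifth subject, no clear study-level stop or required hold applies, except possibly the 13.3 sentence that 13.2 contradicts. Safety reporting applies throughout.

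The fifth-subject threshold assumes that a death counts as a medical complication and that the denominator is subjects so far; neither is defined. The 0.31 is an upper illustration at an assumed 5% risk. It is 0.23 to 0.33 over risks of 3% to 10%, and about 0.05 to 0.15 at 5% once the assumed non-fatal DLTs are added. The conflict between the sections depends on none of these rates. The express treatment of death from DMG in 12.6 is secondary.

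This should be corrected: it concerns the gravest event in a paediatric safety study, and the correction is cheap.

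**What to change.** Reconcile 7.2/12.1, 12.3, 12.6, 13.2 and 13.3 so that together they state:
- one scope of attribution, saying for each of device, microbubbles, drug and disease whether it is in or out, including whether death from DMG counts under 12.6;
- one event count and one study-level action for each class of event, with the same trigger leading to the same action in 13.2 and 13.3;
- for the 20% rule, its denominator, whether a death counts, and stopping probabilities that belong to the rule as worded.

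The content of the rule, including whether a single drug-related event stops or holds the study, is for the sponsor and the DSMC. The cost is a short protocol amendment; no extra subjects, visits or data are needed.

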13. DATA REPORTING/REGULATORY REQUIREMENTS

13.1 Data Reporting

Case Report Forms will be completed for each subject enrolled into the clinical study through an electronic data capture system called Velos. It is the investigator's responsibility for ensuring that all clinical and laboratory data entered on the corresponding CRFs are complete, accurate and authentic.

13.3 Data and Safety Monitoring Committee

To ensure the long-term safety in our study, the investigators will monitor and collect the data for processing and analysis while [name], or another co-investigator physician will be present to assess the safety of the patient during NgFUS application. [name] will oversee the study procedures and will assess the subject's clinical status during therapy. In the case of an allergic or any other reaction to the therapy, the study will be immediately discontinued. Resuscitation equipment will be readily available in the study room, in case of a serious adverse event.

The NCI-approved Data Safety and Monitoring Committee (DSMC) of the Herbert Irving Comprehensive Cancer Center (HICCC) will monitor every subject who receives treatment on this protocol for toxicity. This protocol will adhere to the policies of the currently approved HICCC Data and Safety Monitoring Plan (DSMP), which is in accordance with NCI and CUMC-IRB policy and guidelines. The committee chair is appointed by the HICCC Director. The committee consists of HICCC faculty and staff with expertise in oncology, research pharmacy, research nursing, and data management. The DSMC convenes twice a month to review patient safety and the conduct of the trial. The PI will submit data and safety monitoring reports to the DSMC at a frequency to be determined by the DSMC based on risk to the subjects.

At the time of renewal, the study team will submit the most recent DSMC approval letter for safety review to the CUMC IRB. Any modifications that are required by the DSMC to ensure patient safety will be submitted to the IRB. All protocol deviations, violations, and eligibility waivers will be submitted to and approved by the DSMC prior to being reported to the IRB. All study data reviewed and discussed during these meetings will be kept confidential.

13.4 Quality Control and Quality Assurance

Independent monitoring of the clinical study for protocol and GCP compliance will be conducted periodically by the the departmental QA. Additionally, the Compliance Oversight Committee of the IRB at Columbia University Irving Medical Center may audit the study at any time per institutional policies and procedures. The investigator-sponsor and Columbia University Irving Medical Center will permit direct access of the study monitors and appropriate regulatory authorities to the study data and to the corresponding source data and documents to verify the accuracy of this data.

A risk-based approach will be used by the departmental QA to determine the frequency, number of subject charts, and data elements to be monitored. The departmental QA will review the study status and summarize enrollment, toxicities, SAEs/UPs, dose escalation, statistical endpoints (e.g., stopping rules), etc. for the full DSMC membership at the regularly scheduled meetings.

13.5 Internal On-Site Monitoring

The study Monitoring Visit Log will be completed and signed by the monitor and the PI/CRNP/CRN and/or CRC and will be filed in the regulatory binder.

The departmental QA will communicate with the site coordinator/site Principal Investigator to schedule the monitoring visit and arrange for access to study materials and documentation.

The assigned departmental QA will monitor investigator-initiated trials within 1 month after the first subject is enrolled and throughout the life of the study to ensure that the study is being conducted in accordance with the protocol, GCP, applicable federal and local regulations, and per all applicable SOPs. The departmental QA is responsible to notify the PI and CRNP/CRN/CRC of upcoming monitor visits and convey what information and documentation will be required for the visit(s). The departmental QA is responsible for verifying that informed consent is properly obtained, eligibility is met (via the central registration process), and all study procedures are conducted according to the study protocol. The departmental QA will also verify that the data reported in the CRF's accurately reflect source documents, that all toxicities have been reported to date, and that all SAE's/UPs/deviations/violations have been reported according to local IRB and HICCC DSMC requirements. The departmental QA will issue queries and ensure resolution in a timely and efficient manner. The departmental QA will also monitor for applicable regulatory compliance and research pharmacy compliance (if applicable) and communicate any deficiencies as appropriate.

